9.2.1. Voluntary Withdrawal

Subjects may withdraw from the study at any time. At the time of withdrawal, the Investigator shall document the reason for the withdrawal. For subjects who withdraw from the study and decide to revoke their authorization to use and disclose their medical information, the information that has already been collected in the study record may continue to be used; however, no new information will be obtained or added.

9.2.2. Involuntary Withdrawal

Subjects may be involuntarily withdrawn from the study if the Investigator determines it is in the subject's best interest. If the subject is withdrawn at the investigator's discretion, the reason for withdrawal must be documented in the subject's medical records. Subjects who did not receive the study stent (implant failures) will be followed through hospital discharge and will be considered withdrawn.

9.3. Lost to Follow-up

If a subject fails to return to the clinic and/or is unable to be reached for a follow-up visit the site will attempt to contact the subject and reschedule the missed visit and counsel the subject on the importance of maintaining the assigned visit schedule and ascertain if the subject wishes to and/or should continue in the study.

Before the subject may be considered lost to follow-up, the investigator must make the following attempts to contact the subject:

- Three documented telephone attempts
- One certified letter

If the subject can be reached and no longer wishes to participate in the study, the Investigator shall document the reason for the withdrawal and complete the End of Study eCRF.

If the subject is not able to be reached after the required attempts to contact the subject have been made and the subject has missed two consecutive follow-up visits, or the subject has missed the final post-stent removal visit, the subject may be considered lost to follow-up. The Investigator should document in the subject's medical record the attempts to contact the subject and the reason for withdrawal.

9.4. Subject Status and Classification

A subject will be considered enrolled after a signed informed consent is obtained. An implanted subject participation ends when he or she has completed all phases of the study including the last visit as shown in the Data Collection Schedule or if the study stent is replaced either for planned stent replacement or due to re-intervention. Subjects who are unable to have study stent implanted will be followed through discharge following index procedure and he or she will be considered withdrawn from the study.

9.5. End-of-Study Definition

A clinical study at each participating site is considered completed when participants are no longer being examined or the last participant's last study visit has occurred, and study closeout activities are completed

A subject is considered to have completed the study after he or she has completed all phases of the study including the last visit shown in the Data Collection Schedule (see section 10) or if the study stent is replaced either for planned stent replacement or due to re-intervention.

The end of the study is defined as completion of the final Clinical Study Report.

10. Study Methods

10.1. *Data Collection*

The data collection schedule is shown in Table 10.1. Assessments will be completed based on standard of care practices at the site and PROMIS® pain scale questionnaires will be collected. All study data will be recorded on source documentation and captured within electronic Case Report Forms (eCRFs) for the purposes of this study. Study data will be monitored by Boston Scientific or representatives and as applicable on a regular basis as outlined in the study Monitoring Plan.

Table 10.1: Data Collection Schedule

Procedure/Assessment	Screening/ Enrollment Baseline Visit	Index Procedure (≤ 45 days from Baseline visit)	Post-Procedure Visit	Follow-up Visits		
			Only if Long term indwell of greater than 90 days (45 – 90 ² days from Index procedure)	Stent Removal Visit (< 365 ² days from Index procedure)	Post-Stent Removal visit (3-12 weeks from Stent Removal)	Unscheduled Visit
Informed consent process, including informed consent signature date ¹	X					
Inclusion/Exclusion Criteria	X	X ²				
Demographics	X					
Medical History	X					
Laboratory – Blood Test, Serum Creatinine and Glomerular Filtration Rate (GFR)	X				X ⁵	X
Laboratory – Urinalysis/Culture UTI status and Pregnancy test ⁴	X					X
Physical Assessment: Weight, Height, BMI, and Temperature	X					
QoL Questionnaires (PROMIS®) (Except for UDS):- Adult Short Form v1.0 – Pain Intensity 3a -Adult Short Form v1.0 – Pain Interference 6b	X - Prior to Implant			X - Prior to Removal	X	
Assessment of Adverse Events (including Clavien- Dindo Classification) and Device Deficiencies (including stent migrations and stent dislodgements)		X	X	X	X	X
Stent Performance Assessment		X	X	X		X
Boston Scientific Accessory Device Assessment		X				
Medication Assessment (Antibiotics, NSAIDs, anticholinergic, narcotic/opioid, Diuretic, Phenazopyridine, Alpha blockers)		X - Prior to Discharge				X - Prior to Discharge
Imaging ³						X
COVID-19 Assessment (if available)	X ⁵		X ⁵	X ⁵	X ⁵	X ⁵

1. Informed consent obtained before any study specific, non-standard of care screening tests or procedures are performed
2. See individual stent IFU/DFU for contraindications and maximum indwell time
3. Image to be collected if completed as Standard of care and when suspected of ureteral obstruction
4. Only at the baseline visit
5. Not-required; recommended if available or collected as standard of care

10.2. Study Candidate Screening

All interested subjects will undergo screening during which their eligibility for the study will be determined.

Subjects who do not meet the inclusion/exclusion criteria are considered screen failures. Information on screen failures will be captured in the screening logs and should include reasons for screen failure. These screen failures will not count towards the enrollment ceiling.

If the subject has completed the informed consent process and met all inclusion/exclusion criteria, the subject will progress to the index procedure and follow-up phases of the study, if stent(s) is implanted.

10.2.1. Strategies for Recruitment and Retention

Subjects will be recruited from clinician practice who are receiving device as standard of care. For the completion of post-stent removal follow-up visit, subjects will be compensated for participation in the study, in accordance with pertinent country laws and regulations and per the study site's regulations.

10.3. Informed Consent

Written informed consent must be obtained from all potential study candidates before any study specific, non-standard of care screening tests or procedures are performed. Only current Institutional Review Board (IRB), Ethics Committee (EC) or Research Ethics Board (REB) approved study specific ICF must be used. Study personnel should explain that even if a subject agrees to participate in the study and signs an ICF, certain screening procedures might demonstrate that the subject is not eligible to continue participation. Written informed consent must be recorded appropriately by means of the subject's dated signature.

10.4. Screening Assessments/Procedures

The Screening/Enrollment and Baseline visit may occur on the same day or on different days. The following must be completed prior to collecting baseline data described in section 10.5:

- Informed Consent Process, including informed consent signature
- Review of Inclusion/Exclusion Criteria

10.5. Baseline Visit [up to 45 days prior to Index procedure]

The Baseline Visit will occur prior to the subject having index procedure/stent placement. The assessments below must be completed prior to index procedure and may occur up to 45 calendar days prior to index procedure.

The baseline assessments below can be completed on the same day as Index procedure, prior to the stent implant.

- Demographics: Age, Gender, Race and Ethnicity
- Diagnosis/Medical History (only active medical problems at the time of baseline assessment, including Neoadjuvant chemotherapy (within 6 months prior to stent placement for bladder cancer); Radiation status (pelvis and abdomen))
- Labs: Serum Creatinine, GFR
- Urinalysis/culture: UTI status, Pregnancy test for women of child-bearing potential
- Physical examination: Height, Weight, BMI, Temperature
- COVID-19 assessment: prior diagnosis, test result, vaccination status (if available)
- QoL Questionnaires (PROMIS):
 - Adult Short Form v1.0 – Pain Intensity 3a
 - Adult Short Form v1.0 – Pain Interference 6b

Note: QoL Questionnaires not required for subjects receiving UDS

10.6. Index Procedure –BSC Ureteral Stent Placement

Index procedure is defined as the start time of sedation and/or anesthesia and includes the entirety of the procedure in which the study stent is implanted, however also includes ureteral access sheath insertion, scoping, irrigation, laser lithotripsy, basketing, etc. The stent placement will be performed by a trained physician and per the individual stent IFU/DFU.

Note: Baseline visit information may be collected on same day, prior to the index procedure.

After the index procedure, the following data will be collected:

- Stent Information – type, size, stent laterality (left or right), unilateral or bilateral, time of stent placement
- Stent Performance Assessment – implanted and performed as indicated within IFU/DFU
- Accessory Device Performance and Safety Assessment (BSC Guidewire, BSC Ureteral Access Sheaths {UAS}, BSC Stent Positioner, BSC UDS Accessories) - used during the index procedure
- Medication Assessment (post-procedure) - antibiotics, NSAIDs, anticholinergic, narcotic/opioid, Diuretic, Phenazopyridine, Alpha blockers
- Assessment of Adverse Events (including Clavien-Dindo Classification) and Device Deficiencies (including stent migrations and stent dislodgements)

10.7. Post-procedure Follow-up (only for planned indwell greater than 90 days)

Stent indwell time should be per individual IFU/DFU. If indwell of greater than 90 days is planned, a post-procedure follow-up should be completed between 45 - 90 days from the index procedure as indicated in individual stent IFU/DFU.

The subjects should be followed in clinic for the following data collection:

- Stent Performance Assessment – stent performed as indicated
- Assessment of Adverse Events (including Clavien-Dindo Classification) and Device Deficiencies (including stent migrations and stent dislodgements)
- COVID-19 Assessment: New diagnosis, test result, vaccination status, if available

If indwell of less than 90 days is planned, a post-procedure follow-up is not required.

10.8. Stent Removal Visit (maximum indwell time as indicated in individual stent IFU/DFU)

The stent removal should be per the individual stent IFU/DFU. The indwell time should not exceed indwell period indicated in the individual IFU/DFU. The stent removal shall occur per standard practice.

At the stent removal visit, the following assessments must be performed and data points collected:

- Stent Performance Assessment – performed as indicated during the planned indwell time, as assessed by study physician
- Stent Explant – explant successful; time of explant
- QoL Questionnaires (PROMIS): to be completed before stent removal
 - Adult Short Form v1.0 – Pain Intensity 3a
 - Adult Short Form v1.0 – Pain Interference 6b

Note: QoL Questionnaires not required for subjects receiving Urinary Diversion Stent

- Assessment of Adverse Events (including Clavien-Dindo Classification) and Device Deficiencies (including stent migrations and stent dislodgements)
- COVID-19 Assessment: New diagnosis, test result, vaccination status, if available

If stent is explanted in a non-study clinic facility (e.g., at home, another clinic), the required assessments will be completed via telephone.

If stents are removed inadvertently before intended indwell time, the post-stent removal visit should be completed as indicated in section 10.9 and schedule of events table.

10.9. Post-Stent Removal Visit (Typically, 3 to 12 weeks) from stent removal visit

The post-stent removal visit should occur between 3 – 12 weeks from the Stent Removal Visit. The visit may occur in the office or by telephone. At this visit the following assessments will be performed and data points collected:

- Labs – Serum Creatinine and GFR (not required, collected if office visit and SOC)
- QoL Questionnaires (PROMIS):
 - Adult Short Form v1.0 – Pain Intensity 3a
 - Adult Short Form v1.0 – Pain Interference 6b
- Note: QoL Questionnaires not required for subjects receiving Urinary Diversion Stent
- Assessment of Adverse events (including Clavien-Dindo Classification)
- COVID-19 Assessment: New diagnosis, test result, vaccination status, if available

10.10. Unscheduled Visit

Subjects may have additional visits (other than the study visits specified above), that are unplanned visits and are considered as unscheduled visits. Some examples of these visits may include a visit for a change in symptoms or to check on a medical event that could not be resolved during one of the scheduled study visits.

If an unscheduled visit is for a suspected ureteral obstruction, the following will be attempted to be collected:

- Laboratory Blood test – Serum Creatinine and GFR
- Laboratory Urinalysis – UTI status
- Adverse Event (including Clavien-Dindo Classification) and Device Deficiency (including stent migrations and stent dislodgements) Assessment
- Stent Performance Assessment
- Imaging
- Medication
- COVID-19 Assessment: New diagnosis, test result, vaccination status, if available

10.11. Study Completion

Each subject will be followed to the post-stent removal follow-up visit. All subjects completing the post-stent removal follow-up visit will be considered to have completed the study. Subjects with any ongoing Adverse Events at the end of the study should be followed per institutions SOC.

Upon completion of the study, all adverse events indicated as “ongoing” should be changed to one of the following outcomes:

- Not Recovered/Not Resolved
- Resolved
- Resolved with sequelae
- Unknown

The outcome of “unknown” should only be used for subjects who are lost to follow-up. Whenever possible, sites should enter a reason for each ongoing/unresolved adverse event at time of study exit.

10.12. *Local Laboratory documentation*

The laboratory (blood and urine) analysis, collected in the study will be completed at the local centers per standard of care. Appropriate laboratory certifications and documentation records are required to be maintained at the site.

10.13. *Source Documents*

It is preferable that original source documents are maintained, when available. In lieu of original source documents, certified copies are required to be maintained. A certified copy is a copy (irrespective of the type of media used) of the original record that has been verified (i.e., by a dated signature or by generation through a validated process) to have the same information, including data that describe the context, content, and structure, as the original.

11. Statistical Considerations

11.1. *Endpoints*

11.1.1. Primary Efficacy Endpoint – Technical Success

The primary efficacy endpoint is the technical success of Tria™ in stone management. For all stents except UDS, technical success is defined as stented kidney drains (to bladder) during the planned indwell time with no re-intervention due to obstruction of the stented ureter(s). For UDS, technical success is defined as drainage following stent placement during the planned indwell time with no re-intervention for obstruction. Restenting with a new study stent may only occur during the initial stent placement procedure for such situations as stent misplacement, improper stent size choice, or other conditions, as necessary and will not be considered as a primary effectiveness endpoint failure or a secondary endpoint failure for stricture resolution.

11.1.1.1. Hypotheses

The study will evaluate whether Tria™ stents have technical success during planned indwell in more than 85% in stone management. The null and alternative hypotheses for this evaluation are

$H_0: p \leq 85\%$ $H_1: p > 85\%$

where p is the proportion of stented ureter(s) with technical success.

11.1.1.2. Sample Size

There are two published studies on the patency in the stone management for Double J stents. The success rates were 98% with a 95% CI [94%, 99%] (Calvert, et al., 2013) and 96% with a 95% CI [92%, 99%] (El-Faqih SR, 1991). As a result, an 94% patency rate is estimated as the performance for the Double J stents. The performance goal of 85% is chosen for the patency for TRIA in the stone management, with a non-inferiority margin of 9%.

With a one-sided type I error of 0.025 and a type II error of 0.10 (90% power), a sample size of 127 subjects with Tria™ placed at least 12 hours for stone management are needed to demonstrate the proportion of stented ureters with technical success exceeds 85%. Assuming a 10% attrition rate, at least 142 stone management subjects with Tria™ stent procedures where stents indwell at least 12 hours are required.

11.1.1.3. Statistical Methods

The hypotheses above will be evaluated based on the two-sided 95% exact Clopper-Pearson confidence interval for the proportion of stented ureters with technical success. Only stents placed at least 12 hours will be included in the analysis. If the lower bound of the confidence interval exceeds 85%, the alternative hypothesis will be demonstrated. Sensitivity analysis to missing data will be performed using tipping-point analysis.

In addition, a Generalized Estimating Equation (GEE) model will be used to estimate the technical success rate to account for within-subject correlation due to bilateral stent placement if applicable.

Descriptive statistics including 95% confidence intervals will be utilized to summarize the technical success rates for the non-stone management subjects treated with Tria™ stents respectively.

For non Tria™ ureteral stents in the study, the technical success rates will be summarized by descriptive statistics including 95% confidence intervals by indication (i.e. stone management, benign obstruction, malignant obstruction, ureteral dysfunction, bladder cancer, and other as applicable) respectively for each device type. Only stents placed at least 12 hours will be included in the analysis.

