Inclusion Criteria	
For all ureteral stent types except UDS:
 
 1. Subject is undergoing placement of a Boston Scientific Ureteral Stent(s) included in the registry 2. Subject anatomy is appropriate to accommodate a stent size available in the study 3. Subject is able to accurately detect and report bladder function and pain 4. Subject is willing and able to: 
 a. Complete patient QoL questionnaire at specified time points (for subjects aged \geq 18 years) b. Return for all follow-up visits 
For UDS:
 
 1. Subject is undergoing placement of a Boston Scientific Urinary Diversion Stent(s) 2. The anatomical features of the involved renal collecting system are known by either prior or concurrent urography or axial imaging 3. Subject is willing and able to Return for all follow-up visits
---------------------------	--

8.3. *Exclusion Criteria*

Subjects undergoing placement of a BSC US or UDS who meet any one of the following criteria (Table 8.3) cannot be included in this study or will be excluded from this clinical study. For subjects receiving bilateral/multiple stenting, the final exclusion criterion is confirmed during the stent placement procedure.

Table 8.2: Exclusion Criteria

Exclusion Criteria	
 1. Subject meets any of the contraindications as per individual stent IFU/DFU 2. Subject receiving different stent type in case of bilateral/multiple stenting 3. Subject with an indwelling ureteral stent(s) not planned to be removed prior to/or concurrently with the study stent implant
---------------------------	--

9. Subject Accountability

9.1. *Point of Enrollment*

Subjects will be considered enrolled in the study after he/she signs and dates the informed consent (ICF). No study specific (non-standard of care) procedure(s) or assessment(s) can take place until the informed consent is signed.

9.2. *Withdrawal*

All subjects enrolled in the clinical study (including those withdrawn from the clinical study) shall be accounted for and documented. If a subject withdraws from the study, the reason(s) shall be reported. If such withdrawal is due to problems related to device safety or performance, the investigator shall ask for the subject's permission to follow his/her status/condition outside of the clinical study.

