11.2.2. Control of Systematic Error/Bias

All subjects will be treated according to the directions in the Operating Manual and IFU/DFU.

The primary efficacy endpoint analysis based on the exact Clopper-Pearson confidence interval is specified to be conservative in order to avoid bias towards demonstrating the primary hypothesis (i.e., achieving the performance goal) of the study. Furthermore, the potential of bias from missing data for the primary efficacy endpoint will be assessed through tipping point analysis.

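### The pass/fail interval treats every stented ureter as independent, so bilateral subjects can push the one-sided 2.5% error rate over its limit, and the planned GEE has no say in the decision

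*Combined protocol and SAP*

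**What the plan says.** Section 11.1.1.1 sets the null at 85% and defines the parameter per ureter: "p is the proportion of stented ureter(s) with technical success". Section 11.1.1.3, repeated in the synopsis, says the hypotheses will be "evaluated based on the two-sided 95% exact Clopper-Pearson confidence interval for the proportion of stented ureters with technical success"; a lower bound above 85% means success.

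Bilateral stenting is allowed. The only related exclusion in section 8.3 is "Subject receiving different stent type in case of bilateral/multiple stenting", so a subject with the same stent type on both sides stays in. Section 10.6 collects "stent laterality (left or right), unilateral or bilateral, time of stent placement".

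Section 11.1.1.3 then adds a GEE model, which "will be used to estimate the technical success rate to account for within-subject correlation due to bilateral stent placement if applicable". It states no link function, confidence bound or threshold for that model, and no rule for the case where it disagrees with the exact interval. Section 11.2.2 says the Clopper-Pearson analysis "is specified to be conservative in order to avoid bias towards demonstrating the primary hypothesis".

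The sample size section counts people rather than ureters: "a sample size of 127 subjects with" Tria in place for at least 12 hours, raised to 142 for 10% attrition.

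**The concern.** Clopper-Pearson has guaranteed coverage when the success count is binomial, that is, when the units are independent with a common success rate. Two ureters in one person share anatomy, stone disease and operator, and the plan itself expects them to be correlated. Positive correlation makes the success count more variable than the binomial, so the lower bound clears 85% by chance more often than the nominal calculation allows.

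This is the one test in the registry with a pass/fail outcome; section 11.1.2.1 sets none for safety. As written, the unadjusted interval decides even if the GEE points the other way. The assurance in section 11.2.2 also covers a case in which it need not be true. Choosing a GEE bound after seeing the data would not repair this, because the result depends on the scale of the bound.

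**Working it through.** **Inputs.** From sections 11.1.1.1 to 11.1.1.3: null rate 0.85, assumed rate 0.94, one-sided 2.5%, power 90%, 127 subjects (142 with attrition), decision by the Clopper-Pearson lower bound on ureters. Assumed, because the documents do not give them: the number of bilateral subjects *b* and the within-subject correlation *ρ*.

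**The plan's own figure.** With one ureter per subject and n = 127, the smallest count whose lower bound exceeds 85% is 116. P(X ≥ 116) is 2.45% at p = 0.85 and 92.0% at p = 0.94. At n = 126 the power is 86.4%. So 127 is right for one ureter per subject, and 127/0.9 = 141.1 rounds up to 142. The slack below 2.5% at 127 is only 0.05 percentage points.

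**With bilateral subjects.** Let K subjects include *b* bilateral ones, giving n = K + b ureters. The K − b unilateral ureters are binomial. For each pair:

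- P(both succeed) = p² + ρp(1−p)
- P(exactly one) = 2(1−ρ)p(1−p)
- P(neither) = (1−p)² + ρp(1−p)

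At p = 0.85 and ρ = 0.5 these are 0.78625, 0.1275 and 0.08625. Convolving the pieces and summing from the Clopper-Pearson cut-off for n ureters gives the exact type I error:

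| Subjects | Bilateral | Ureters | Cut-off | ρ = 0 | ρ = 0.5 | ρ = 1 |
|---|---|---|---|---|---|---|
| 127 | 0 | 127 | 116 | 2.45% | 2.45% | 2.45% |
| 127 | 9 | 136 | 124 | 2.33% | 2.69% | 3.06% |
| 127 | 25 | 152 | 138 | 2.44% | 3.38% | 4.40% |
| 142 | 10 | 152 | 138 | 2.44% | 2.81% | 3.19% |
| 142 | 28 | 170 | 154 | 2.18% | 3.06% | 4.02% |
| 142 | 43 | 185 | 167 | 2.38% | 3.71% | 5.15% |

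The driver is the variance inflation 1 + 2bρ/n. For 25 of 127 bilateral it is 1 + 25/152 = 1.16 at ρ = 0.5 and 1 + 50/152 = 1.33 at ρ = 1.

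**All bilateral counts up to one third** (1–42 of 127, 1–47 of 142):

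| ρ | Type I error | Counts above 2.5%, 127 subjects | Counts above 2.5%, 142 subjects |
|---|---|---|---|
| 0 | 1.3–2.5% | 0 of 42 | 0 of 47 |
| 0.25 | 1.4–3.1% | 11 of 42 | 12 of 47 |
| 0.5 | 1.4–3.75% | 21 of 42 | 24 of 47 |
| 1 | 1.4–5.3% | 31 of 42 | 37 of 47 |

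The pattern is a saw-tooth, because the cut-off is a whole number. At ρ = 0.5, 24 of 127 bilateral gives 2.0% and 25 gives 3.4%. Few bilateral subjects can be harmless: 1–8 of 127 stays at or below 2.34% even at ρ = 1.

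**Candidate repairs.** Same counts, ρ = 0, 0.25, 0.5, 0.75 and 1, full enumeration of outcomes:

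- Clopper-Pearson on the effective sample size: 1.3–2.44%
- Logit-scale cluster-robust bound: 1.3–2.46%
- Proportion-scale robust Wald bound: 3.5–5.6%, above 2.5% in every case

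**The case against.** The plan does recognise the clustering and pre-specifies a GEE, so readers of the report will see both results. The harm depends on two unknown inputs, and modest values give little or none. Averaged over 110–142 analysed subjects at correlation 0.5, the type I error is 1.99% with 5% bilateral and 2.26% with 10%. With no bilateral subjects nothing changes. All of this is true, and it rules out any claim of certain or large inflation. It does not give the GEE a role in the decision, and at 20% and 30% bilateral the same averages are 2.67% and 3.06%.

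Results at exactly 127 or 142 also do not carry over to other counts, and attrition and the 12-hour rule will move the analysed number. At 128 subjects, 1–8 bilateral reaches 2.65% at correlation 0.5. That supports the concern, since chance then decides whether the level holds.

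The repair is itself approximate. Across 110–142 subjects the effective-sample-size rule can slightly exceed the limit: 2.56% at 122 subjects, 5 bilateral, correlation 1, without the small-sample factor K/(K−1), and 2.55% at 111 subjects, 8 bilateral, correlation 1, with or without it. This stands, but it is far below the unadjusted rule's 5.3%.

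The loss of power also stands and should be written into the plan. Reassurance based on 142 analysed subjects assumes no attrition.

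**Conclusion.** The concern holds. The hypothesis and the deciding interval are per ureter, same-type bilateral subjects are eligible, and neither the one-sided 2.5% level nor the conservatism statement is assured once correlated pairs enter the analysis. For up to one third bilateral, the type I error at 127 or 142 subjects ranges from 1.3% to 5.3% across correlations 0 to 1. Part of that range lies below 2.5%, and the bilateral share and correlation are assumptions, so the finding is that the level is not guaranteed, not that it will be exceeded. The sample size of 127 is not in error for one ureter per subject. The point should be settled before analysis but does not undermine the design.

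**What to change.** **Section 11.1.1.3.** State that if any analysed subject contributes more than one ureter, the deciding lower bound is the Clopper-Pearson bound computed on x/D successes out of n/D. Here x is the number of successful ureters, n the number of ureters, and D the cluster-robust variance of the proportion (subject as cluster) divided by p̂(1−p̂)/n. Floor D at 1, set it to 1 when p̂ = 1, and say whether the K/(K−1) factor is applied. The plain interval is then supportive. If no subject contributes more than one ureter, the plain interval decides as now.

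An acceptable alternative is a cluster-robust GEE lower bound explicitly on the logit scale. A proportion-scale Wald bound should not be used. One outcome per subject would also be exact, but the 85% and 94% would have to be restated per subject. If 94% remained the per-ureter rate, power at 127 subjects with 20% bilateral would be 87.0% at correlation 0.5.

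**Section 11.2.2.** Limit the conservatism statement to one ureter per subject.

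**Section 11.1.1.2.** Say that 127 assumes one ureter per subject, and add a note on power.

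**Cost.** This is SAP wording only, since laterality is already collected. Power at a true rate of 94%, plan's rule versus effective-sample-size rule:

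| Subjects | Bilateral | ρ = 0.5 | ρ = 1 |
|---|---|---|---|
| 127 | 25 | 94.7% vs 89.0% | 93.5% vs 84.5% |
| 142 | 28 | 96.2% vs 92.9% | 95.2% vs 88.5% |

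With 142 analysed subjects, power at correlation 0.5 stays at or above 91.0% for every bilateral count up to one third. With 127 it can fall below the planned 90%.
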